5.5. Concordance Assessments

The concordance between the surgeon's conspicuity and the blinded reader's conspicuity will be assessed in three ways.

5.5.1. Treatment Effect on Conspicuity per Surgeons Review

The first approach is to evaluate the treatment effect based on the surgeons conspicuity score. The objective for this analysis is to check if the conclusion of treatment effect shown from the central readers rating can be confirmed by the surgeons reading. If the answer is a 'Yes' then one can conclude that concordance is achieved. Hence, this analysis serves as a confirmatory analysis of the primary analysis. In additional, we can also compare the magnitude of treatment effect (expressed as the odds ratio) between the primary analysis and confirmatory analysis. All subjects with ≥ 1 missing data from surgeon will be excluded from this analysis.

Procedure and summary table (**Table 14.2.5.1**) for this confirmatory analysis will follow the same GEE approach described in [Section 5.1](#), however, the nominal p-values will be displayed as is without control for multiplicity.

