5.5.2. Covariate Analysis

The second approach is to pool the conspicuity scores from both surgeon and blinded reader into a single dataset and add a new covariate (evaluator) into the GEE model; the purpose is to assess if the effect of evaluator is or is not a statistically different covariate. A summary table (**Table 14.2.5.2**) will include the results from the following covariate analysis. All subjects with ≥ 1 missing data from either surgeon or central reader will be excluded from this analysis.

To perform this analysis, a new variable (rater: surgeon vs central reader) and interactions will be added to the full model (**Model 3**) and Reduced model (**Model 4**). Score statistics for Type 3 GEE analysis will be used to determine if the rater is statistically significant factor.

```

PROC GENMOD DATA=resp descending;
  CLASS usubjid ureter(ref='Right') Rater(ref='Surgeon')
        TRT(ref='Saline');
  MODEL conspicuity = trt ureter rater
                     trt*ureter rater*ureter rater*trt
                     Rater*ureter*trt
                     /LINK=clogit DIST=mult TYPE3;
  REPEATED subject = usubjid / type=ind;
Run;

PROC GENMOD DATA=resp descending;
  CLASS usubjid ureter(ref='Right') Rater(ref='Surgeon')
        TRT (ref='Saline');
  MODEL conspicuity = trt ureter rater
                     /Link=clogit DIST=mult TYPE3;
  REPEATED SUBJECT = usubjid / type=ind;
Run;
Where rater will be coded as (central vs surgeon).

```

(Model 3) (Model 4)

This covariate analysis will be performed only for the comparisons between the IC treatment vs the Saline treatment. Each GEE model will be fitted separately for each comparison.

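### SAP 5.5.1 concludes surgeon–reader concordance from a shared treatment effect, which does not measure agreement between paired scores

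*SAP*

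**What the plan says.** SAP Section 2.1.1 lists concordance of the conspicuity scores between surgeons and blinded central reviewers among the other efficacy endpoints. Section 5.5 opens: "The concordance between the surgeon's conspicuity and the blinded reader's conspicuity will be assessed in three ways".

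- **Section 5.5.1** refits the Section 5.1 GEE model to the surgeons' scores, in order to "check if the conclusion of treatment effect shown from the central readers rating can be confirmed by the surgeons reading". The rule follows: if so, "then one can conclude that concordance is achieved". It adds that "we can also compare the magnitude of treatment effect (expressed as the odds ratio) between the primary analysis and confirmatory analysis", but gives no criterion for that comparison.
- **Section 5.5.2** pools both evaluators' scores and adds a rater term: "the purpose is to assess if the effect of evaluator is or is not a statistically different covariate". The criterion is a score test: "Score statistics for Type 3 GEE analysis will be used to determine if the rater is statistically significant factor". The full model (Model 3) also carries the rater-by-treatment interaction.
- **Section 5.5.3**, using the definition in Section 3.8.5, pairs surgeon and central scores by treatment and ureter and counts a pair as agreeing if it differs by at most 1 point. Table 14.2.5.3 shows n (%) of agreeing pairs. The planned test is whether agreement is associated with treatment and ureter. No minimum level of agreement is set.

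Section 5.1 states that the surgeon is not blinded to saline versus IC, only to the IC dose.

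**The concern.** Agreement is a property of the pair of scores given to the same ureter after the same injection. The 5.5.1 rule looks at something else: whether each evaluator, taken separately, rates IC above saline on average. Two evaluators can both do so and still disagree ureter by ureter.

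The unblinded surgeon weakens the rule further. SAP Section 3.1 says IC is expected to outperform saline, so a surgeon who knows the injection may show an IC effect partly from expectation. That effect is weak evidence that the surgeon's scores match those of blinded readers.

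At stake is a listed endpoint. Followed as written, the rule lets a report state that concordance was achieved whatever Table 14.2.5.3 shows.

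**Working it through.** The documents give no expected agreement rate, threshold or power for concordance, and the sample-size assumptions are redacted. There is no plan figure to reproduce, so the check is of the logic.

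**1. An argument that needs no assumed distribution.** Take the surgeons' data within one dose group and reassign each subject's set of four surgeon scores to a different subject. The 5.5.1 model contains only treatment and ureter, with subject as the cluster. Its odds ratio, robust standard error and p-value are therefore unchanged, and so is the 5.5.1 conclusion. The pairing with the central readers' scores has been destroyed. The rule cannot tell the two datasets apart.

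**2. Simulation inputs.**
- Subjects: 116 − 21 = 95 for efficacy (SAP 3.2). 95 / 2 = 47.5, so 47 per dose. The 1:1 split is assumed from SAP 3.7, where the saline group is expected to be twice each dose group.
- Pairs per comparison: 47 × 2 treatments × 2 ureters = 188.
- Models: proportional-odds GEE, independence working correlation, score test, in the reduced forms (Model 2 for each evaluator, Model 4 pooled).
- Significance: two-sided 0.05, assumed because 5.5.1 names no level.
- Scores: integers, pairs independent within subject, 200 replicates per scenario. All distributions are assumed.

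**3. Scenarios.**
- A: every pair differs by at least 2 points, in random direction.
- B: evaluators independent given treatment. Probabilities for scores 1 to 5 are saline (0.35, 0.30, 0.20, 0.10, 0.05), and the reverse for IC.
- C: central scores as in B, surgeon 1 point higher in 35% of pairs, capped at 5.
- D: surgeon always 2 points higher.

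| | Pairs within 1 point | Weighted kappa, saline / IC | Both IC effects significant | Rater p > 0.05 |
|---|---|---|---|---|
| A | 0% | −0.77 / −0.79 | 100% | 96% |
| B | 65% | 0.01 / 0.00 | 100% | 96% |
| C | 100% | 0.89 / 0.91 | 100% | 0% |
| D | 0% | 0.14 / 0.18 | 100% | 0% |

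Taking significance for both evaluators as confirmation, the 5.5.1 rule gives the same answer in all four. The paired statistics separate them. The rater test is not a test of agreement in either direction: it is usually non-significant in A and B and always significant in C. It does catch the systematic shift in D.

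**4. Why the within-1-point rate needs a companion.** For scenario B, exact agreement by chance is 0.1225 + 0.09 + 0.04 + 0.01 + 0.0025 = 0.265. Adjacent scores add 2 × (0.105 + 0.06 + 0.02 + 0.005) = 0.38. The total is 0.645, against 0.649 simulated. Two evaluators scoring uniformly at random would reach (5 + 8) / 25 = 52%.

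**5. A second assumed set.** With saline (0.40, 0.35, 0.20, 0.05, 0), IC (0.05, 0.05, 0.20, 0.40, 0.30) and independent evaluators, both effects were significant in 400 of 400 trials, with mean within-treatment kappa 0.01 (saline) and 0.00 (IC).
- Expected share within 1 point: saline 0.325 + 0.44 = 76.5%; IC 0.295 + 0.425 = 72%.
- Pooled over treatments, the means are 1.9 and 3.85. The between-treatment variance is (1.95 / 2)² = 0.951 and the average within-treatment variance is (0.79 + 1.1275) / 2 = 0.959. Weighted kappa is therefore about 0.951 / 1.909 = 0.50.

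The pooled value comes entirely from the treatment effect, so a chance-corrected statistic has to be computed within treatment.

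**The case against.** The strongest reply is that Section 5.5.3 already supplies a paired measure. Zero agreement would show as 0% in a pre-specified table. That stands, and a reader who infers from 5.5.1 that the SAP has no agreement measure would be wrong. It does not cure 5.5.1: no sentence ties the 5.5.1 conclusion to Table 14.2.5.3, and the 5.5.3 test asks whether agreement varies with treatment and ureter, not whether it is adequate.

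A reader might also infer that Section 5.5.2 treats a non-significant rater term as proof of agreement. The SAP does not write that. It says only that the test will determine whether rater is a significant factor, and Model 3 already examines whether the evaluators differ by treatment. What remains is a caution on interpretation.

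A third reply is that 5.5.1 means concordance of conclusions, since it calls itself a confirmatory analysis of the primary result. That reading is possible. However, the endpoint in Section 2.1.1 and the opening of Section 5.5 concern concordance of the scores, so the unqualified conclusion will be read that way.

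Finally, the simulations rest on assumed, large effects. Independent scoring means no agreement beyond chance within treatment; it does not mean no agreement, since 65% to about three quarters of such pairs meet the SAP's own 1-point definition. Literal zero agreement needs constructions such as A or D. Scenario A is extreme and shows only what is possible.

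**Conclusion.** The concern holds for Section 5.5.1. Its rule compares group-level conclusions, one of them from an evaluator who knows the treatment, and can declare concordance when paired agreement is poor or no better than chance within treatment. The reassignment argument establishes this without assumptions about the scores. The 100% figures depend on the assumed distributions and are illustrative; they do not predict this trial's agreement.

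The documents do not support the stronger inference that concordance goes unmeasured or that the efficacy conclusion is at risk. Section 5.5.3 measures paired agreement, and nothing in the primary analysis depends on Section 5.5. Section 3.4 confines type I error control to the primary endpoint, and 5.5.1 says its own "the nominal p-values will be displayed as is without control for multiplicity". The point should be corrected, but it is not a threat to the primary result.

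**What to change.** 1. In 5.5.1, delete the conclusion that concordance is achieved. State instead that the surgeon data do or do not support the primary treatment-effect conclusion.
2. Base any concordance statement on the 5.5.3 pairs. Report the within-1-point agreement rate with a 95% CI that allows for several pairs per subject. Add a chance-corrected statistic computed within treatment.
3. Choose a statistic that accepts half-points. Central scores are averages of two readers when those are within 1 point, while surgeons give whole numbers. An absolute-agreement ICC with a subject-clustered or bootstrap CI would do.
4. If a yes/no concordance conclusion is wanted, state the required level of agreement in advance.
5. Optionally, report the rater and rater-by-treatment odds ratios with 95% CIs from Models 3 and 4, and note that a non-significant rater term is not evidence of agreement.

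The cost is a few lines of SAP text and some added statistics from data already collected. A chance-corrected coefficient can be low when nearly all scores within a treatment are alike, so it should be read beside the agreement rate. The concordance claim may become weaker as a result.

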5.5.2. Covariate Analysis

The second approach is to pool the conspicuity scores from both surgeon and blinded reader into a single dataset and add a new covariate (evaluator) into the GEE model; the purpose is to assess if the effect of evaluator is or is not a statistically different covariate. A summary table (**Table 14.2.5.2**) will include the results from the following covariate analysis. All subjects with ≥ 1 missing data from either surgeon or central reader will be excluded from this analysis.

To perform this analysis, a new variable (rater: surgeon vs central reader) and interactions will be added to the full model (**Model 3**) and Reduced model (**Model 4**). Score statistics for Type 3 GEE analysis will be used to determine if the rater is statistically significant factor.

```

PROC GENMOD DATA=resp descending;
  CLASS usubjid ureter(ref='Right') Rater(ref='Surgeon')
        TRT(ref='Saline');
  MODEL conspicuity = trt ureter rater
                     trt*ureter rater*ureter rater*trt
                     Rater*ureter*trt
                     /LINK=clogit DIST=mult TYPE3;
  REPEATED subject = usubjid / type=ind;
Run;

PROC GENMOD DATA=resp descending;
  CLASS usubjid ureter(ref='Right') Rater(ref='Surgeon')
        TRT (ref='Saline');
  MODEL conspicuity = trt ureter rater
                     /Link=clogit DIST=mult TYPE3;
  REPEATED SUBJECT = usubjid / type=ind;
Run;
Where rater will be coded as (central vs surgeon).

```

(Model 3) (Model 4)

This covariate analysis will be performed only for the comparisons between the IC treatment vs the Saline treatment. Each GEE model will be fitted separately for each comparison.

5.5.3. Dichotomization of the Difference in Conspicuity

The third approach is to dichotomize the difference in conspicuity between the surgeon and the blinded reader. The four scores from the surgeon will be paired with the four scores from the blinded central reader based on treatment and ureter for a given subject. Based on the difference in the paired conspicuity (see [Section 3.8.5](#)) a concordance response variable will be derived for each pair of the conspicuity:

- a. the ratings are in agreement when the difference in score is (+1, 0, -1), otherwise
- b. the ratings are not in agreement when the difference is more than +/- 1 point

The association of this concordance response variable (agree vs not agree) with treatment and ureter will also be evaluated using the GEE model based on the concept of logistic regression for dichotomized response. In case of missing data that prevent from forming a pair of observations to derive this concordance response variable, the data will be excluded from this analysis.

The score statistics will be used to determine if the treatment is statistically associated with this dichotomized response. The following is an example of SAS syntax for this analysis between the IC Hight dose vs Saline. This analysis will be performed separately for each comparison (IC High dose vs Saline, IC Low dose vs Saline, and IC High dose vs IC Low dose). All subjects with ≥ 1 missing data from either surgeon or central reader will be excluded from this analysis.

```

PROC GENMOD DATA=dischotH descending;
CLASS usubjid ureter(ref='Right') TRT(ref='Saline');
MODEL response (event='Y') = trt ureter trt*ureter
                           /LINK=LOGIT DIST=BINOMIAL TYPE3; (Model 5)
REPEATED subject = usubjid / type=EXCH;
ESTIMATE 'OR: IC vs Saline' trt 1 -1 / exp;
Run;

```

```

PROC GENMOD DATA= dischotH descending;
CLASS usubjid ureter(ref='Right') TRT(ref='Saline');
MODEL response (event='Y') = trt ureter
                           /LINK=LOGIT DIST=BINOMIAL TYPE3; (Model 6)
REPEATED SUBJECT = usubjid / TYPE=EXCH;
ESTIMATE 'OR: IC vs Saline' trt 1 -1 / exp;

```

Where:

1. 'TRT' is coded to IC or Saline
2. 'URETER' is coded to 'Left' or 'Right'
3. 'USUBJID' is the unique Subject Identification
4. REPEATED statement controls the intra-subject correction due to repeated measures. In this example, exchangeable working correlation structure is used (TYPE=EXCH).

The analysis summary table (**Table 14.2.5.3**) will include distribution of number (%) of pairs that are in agreement vs not in agreement in each treatment group by ureter (left vs right), score statistics for Type 3 GEE analysis, odds ratio estimates, and 95% confidence intervals for the odds ratio between IC High Dose vs Saline, IC Low dose vs Saline and IC High dose vs IC Low dose (an exploratory analysis). All nominal p-values will be displayed as is without control for multiplicity.

5.6. Covariate Analysis and Subgroup Analysis

The impact of some potential covariates on the primary efficacy endpoint will be evaluated if data warrants. The potential covariates include but not limited to

1. Surgery type
2. Surgeons specialty type
3. Age and age group, sex, race group

Each variable will be assessed individually by adding the variable to the primary efficacy models described in Section 5.1.

Similarly, if data warrants, subgroup analyses defined by the above variables will be performed. All those analyses, if performed, will be exploratory/ confirmatory.

6. PHARMACOKINETICS EVALUATIONS

PK portion of the study are dropped. Hence, all previously defined PK analyses are no longer applicable.

7. SAFETY AND TOLERABILITY EVALUATIONS

Safety data summaries will be displayed by randomization group for clinical safety laboratory test and ECG; adverse events and vital signs will be tabulated by treatment groups. Safety data listing by individual subject will be prepared for all safety endpoints.

7.1. Total Exposure

All subjects are expected to receive a dose of normal saline and a dose of IC. Hence, no formal total exposure in terms of number of doses or treatment duration will be applied.

7.2. Adverse Events

Adverse events reported from Day 1 beginning at the Saline injection through the final follow-up will be considered treatment emergent adverse events (TEAEs). **Adverse event reported after Saline injection and prior to IC injection will be mapped to Saline treatment, all adverse events after IC injection, including events reported during the follow period will be mapped to IC treatment. For all AEs, if the onset date is missing/partial, the AE is TEAE and will be mapped to IC study unless the available portion of the date/time indicates otherwise.**

The Medical Dictionary for Regulatory Activities (Version 22) will be used to classify all AEs with respect to system organ class and preferred term.

The following summary tables will be produced for the TEAEs. All data summaries will provide number (%) subjects as well as total number of events in each category by treatment group (IC High, IC Low, and Overall).

1. a topline summary of TEAEs (**Table 14.3.2.1**)
2. a summary table by preferred term in descending order of total incidence (**Table 14.3.2.2**)
3. a summary table by system organ class and preferred term (**Table 14.3.2.3**)
4. a detailed summary table by system organ class, preferred term and severity (**Table 14.3.2.4.1**)
5. a detailed summary table by system organ class, preferred term and relationship (**Table 14.3.2.4.2**)
6. a table of serious TEAEs by system organ class and preferred term (**Table 14.3.2.5**)
7. TEAE leading to study discontinuation (**Table 14.3.2.6**)

In addition, adverse event of special interest (**Table 14.3.2.7**) will be identified and summarized if data warrant. Adverse event of special interest (AEOSI) could include but not limit to transient elevation of blood pressure and reflex bradycardia. For example, TEAE of tachycardia, hypotension, hypertension, rash or erythema, respiratory symptoms, such as dyspnea or

bronchospasm will be flagged as AEOSI. All adverse events will be reviewed before database lock to identify all AEOSI in the study.

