The study will enroll approximately 116 subjects from approximately 10 – 20 study centers in the United States. Subjects scheduled for urological or gynecological surgical procedures, age 18 to 85 years inclusive, will be screened for participation. Screening will occur within 30 days before study drug administration (Day of Surgery). After signing the informed consent, medical history, physical examination, baseline laboratory testing, pregnancy testing, 12-lead ECG, and vital sign measurements will be completed during the screening visit. Any procedure done for the purpose of the surgery before the date of signing the informed consent may be used as long as it was within 30 days of the scheduled surgery date.

On the day of surgery (Day 1) the subject will be evaluated for eligibility for randomization. Eligible subjects will be randomized to receive a dose of either IC high dose (5 mL) or IC low dose (2.5 mL). Each randomized subject will serve as his/her own control by receiving a dose of normal saline prior to receiving the randomized IC dose. The surgeon will be blinded to the IC dose a subject receives. Time of injection of saline and IC will be captured.

To evaluate the efficacy outcomes, each subject will first be injected intravenously with 5 mL 0.9% saline. The ureteral orifices/flow will be observed and video recorded for 10 mins. The time period that will be captured on video is from injection to 10 minutes post injection. If both ureters cannot be visualized simultaneously, then alternating 15-30 second images of each ureter or ureteral orifice will be obtained. The process will be repeated in the same patient for the IC dose. Hence, each subject will have 2 videos and each will be about 10 minutes in length.

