Protocol Schedule of Assessment is included here for the convenience of review.

Table 1: Schedule of Assessments

	Screening period Day -30 to -1 ¹	Randomization/ Treatment Day 1	Follow-up Visit Day 7 to Day 32 or Early Termination ²	Telephone follow-up if Follow-up visit prior to Day 28
Informed Consent	X			
Inclusion / Exclusion Criteria	X	X		
Medical, surgical history, demography, medication review	X			
Physical Examination	X		X	
Height	X			
Weight	X			
Vital Signs	X	X ³	X	
12 Lead ECG	X		X	
Randomization		X		
Concomitant Medications	X	X	X	X
AE/SAE		X	X	X
Blood Safety Labs ⁴	X		X ⁵	
PK Blood ⁶ , Urine ⁷ , and Stool ⁸ collection		X		
Bowel Prep ⁹ (PK group)	X (Day -1)			
Surgery		X		
Surgeon satisfaction with IC treatment		X		
0.9% saline injection		X		
0.8% IC injection		X		
Video filming of ureteral jet flow with saline and with IC		X		
Surgeon conspicuity score of urine Jet flow		X ¹⁰		
Urine Pregnancy Test ¹¹		X		

1. Bloodwork/ECG completed as part of the pre-operatively work-up (within 30 days of surgery) will be acceptable for study use and will not have to be repeated for study participation.
2. Subjects who have onsite visit between Day 7 and 27 may have safety follow-up completed with an additional telephone call between Day 28-32.
3. Continuous monitoring, including heart rate and rhythm, will be required during the procedure and in the immediate post-operative period, vital signs will be collected for the study at the following specific time points: immediately prior to each injection and 5 minutes after each injection and thereafter approximately every 15 minutes through 1 hour following the procedure
4. Blood Safety Labs: hematology = White blood cell count (WBC), Red blood cell count (RBC), Hemoglobin, Hematocrit, platelets, differential blood count (Neutrophils, lymphocytes, monocytes, eosinophils, basophils). Serum chemistry = total bilirubin, AST, ALT, alkaline phosphatase (ALP), creatinine, blood urea nitrogen, sodium, chloride, potassium, bicarbonate, phosphorus, calcium, glucose, albumin.
5. Must be performed at the same laboratory as the initial bloodwork.
6. For approximately 16 Subjects at 2 planned sites blood plasma collection will occur prior to and post IC injection at 2, 5, 7, 10, 15, 20, 30, and 40 mins, then at 1, 2, 3, 4 hours after IC administration.

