3.5. Procedures for Handling Missing Data

Missing or partial data associated with efficacy assessments will be discussed specifically within each section. No missing data imputation will be performed for safety parameters. However, AEs with missing severity assessments will be tabulated as “severe,” and AEs with missing relationship assessments will be tabulated as “related” for the purpose of analysis; and the missing data will be presented in data listing as is.

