3.7. Treatment Group vs Randomization Group

All qualified subjects will be randomized to either a dose of 2.5 mL IC (referred to as the Low dose) or a dose of 5.0 mL IC (referred to as the High dose). All randomized subjects will receive a dose of normal saline before receiving the randomized IC dose.

Hence, there are 2 randomization groups, namely IC High Dose and IC Low Dose and 3 treatment groups (IC High dose, IC Low dose, and Saline) in this study.

If a dosing error occurred (e.g., a subject was randomized to the IC High dose but actually received IC Low dose, and vice versa), the subject will be included in the actual treatment group received for efficacy, PK, and safety analyses; this will be an important protocol deviation and the incident will be clearly documented in the study report and in the database.

Data presentation for study population, physician overall satisfaction, safety lab, and 12-ECG will be based on the 2 randomization groups; whereas the data presentation for conspicuity, TTV, adverse events, and vital signs will be based on the 3 treatment groups. A Study Overall group may be included in certain data presentations (e.g., demographics) if data warrant. The Saline group will include all subjects who had saline dose, hence, the number of subjects in this treatment group will expect to be twice the size of IC Low dose and IC High dose. If data warrants, the Saline group may also be split by IC dose group. That is, subjects received the IC Low dose vs subjects received the IC High dose.

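### The adverse event mapping gives saline only the gap between the two injections and IC everything to about Day 30, so any saline-versus-IC AE comparison is confounded with surgery and recovery; the timing key and the table columns also need reconciling.

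*SAP*

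**What the plan says.** **Mapping.** SAP Section 7.2 has two limbs. For saline: "Adverse event reported after Saline injection and prior to IC injection will be mapped to Saline treatment". For IC: "all adverse events after IC injection, including events reported during the follow period will be mapped to IC treatment".

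**Missing data.** In the same paragraph, "if the onset date is missing/partial, the AE is TEAE and will be mapped to IC study", unless the known part of the date or time shows otherwise. Under Section 3.5, "AEs with missing relationship assessments will be tabulated as" related.

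**Design.** Section 2 fixes the order: "Each randomized subject will serve as his/her own control by receiving a dose of normal saline prior to receiving the randomized IC dose". On the filming that follows each injection: "The time period that will be captured on video is from injection to 10 minutes post injection". A footnote to Table 1 sets the end of follow-up: "Subjects who have onsite visit between Day 7 and 27 may have safety follow-up completed with an additional telephone call between Day 28-32".

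**Presentation.** Section 3.7 says "the data presentation for conspicuity, TTV, adverse events, and vital signs will be based on the 3 treatment groups", and one of those three groups is Saline. Section 7 says only that AEs are tabulated by treatment groups. Section 7.2 lists the TEAE table columns as IC High, IC Low and Overall, with no Saline column. Section 7.1 plans no exposure summary by number of doses or duration, because each subject is expected to receive one dose of each agent.

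**The concern.** Saline is the within-subject control, and Section 3.7 puts it beside the two IC doses for AEs. The two periods being compared are very different. The saline period is a short stretch during the procedure. The IC period takes in the rest of surgery, emergence, recovery and about a month at home. Ordinary surgical events will fall almost entirely under IC whatever the drug does, and the defaults for missing onset and missing relationship push the same way.

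Two wording problems add to this. The TEAE definition and the saline limb turn on when an event is reported, while the missing-data sentence turns on onset. For a symptom that starts before IC but is voiced only after anaesthesia or sedation, the two keys give different answers. In addition, if the Section 7.2 columns apply, an event mapped to saline has no stated column.

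Safety is the first secondary objective. The acute events that Section 7.2 lists as of special interest (blood pressure and heart rate changes, rash, dyspnea, bronchospasm) are those for which the patient's own saline period could be informative.

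**Working it through.** The SAP gives no calculated AE figure, so there is nothing to reproduce. The check is how large an IC excess the mapping produces when neither agent has any effect.

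**Inputs from the SAP.** Saline window: saline injection to IC injection (7.2). IC window: IC injection to final follow-up at Day 28 to 32 (7.2 and Table 1), which is 27 to 31 days after Day 1. Video length: 10 minutes (2). Sample size: about 116 (2).

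**Assumptions.** The saline-to-IC gap g is 10 minutes (the video length), with 30 minutes as an alternative. The proportion p with any AE over 29 days is 30% or 50%. For early clustering, a share f of 25% or 50% of the event hazard falls evenly in the first T = 60 or 120 minutes after the saline injection.

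**1. Window ratio** = [(D − 1) × 1440 − g] / g.

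| Gap | Day 28 | Day 30 | Day 32 |
|---|---|---|---|
| 10 min | 38,870/10 = 3,887 | 41,750/10 = 4,175 | 44,630/10 = 4,463 |
| 30 min | 38,850/30 = 1,295 | 41,730/30 = 1,391 | 44,610/30 = 1,487 |

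Saline holds about 0.02% to 0.08% of the AE observation time.

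**2. Null expectation, constant hazard, g = 10.** Hazard λ = −ln(1 − p)/(29 × 1440). Expected subjects = 116 × [1 − exp(−λ × window)].
- p = 30%: 0.0099 under saline, 34.8 under IC (both doses pooled).
- p = 50%: 0.0193 under saline, 58.0 under IC.

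The subject ratio is about 3,000 to 3,500 to 1.

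**3. Null expectation, early clustering.** With H = −ln(1 − p), saline = 116 × [1 − exp(−H f g/T)] and IC = 116 × [1 − exp(−H(1 − f g/T))]. The small saline contribution from the unclustered share is ignored.

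| p | f | T (min) | Saline, g = 10 | IC, g = 10 | Ratio, g = 10 | Ratio, g = 30 |
|---|---|---|---|---|---|---|
| 30% | 25% | 60 | 1.7 | 33.6 | 20 | 6.1 |
| 30% | 25% | 120 | 0.9 | 34.2 | 40 | 13 |
| 30% | 50% | 60 | 3.4 | 32.4 | 9.5 | 2.8 |
| 30% | 50% | 120 | 1.7 | 33.6 | 20 | 6.1 |
| 50% | 25% | 60 | 3.3 | 56.3 | 17 | 5.5 |
| 50% | 25% | 120 | 1.7 | 57.2 | 34 | 11 |
| 50% | 50% | 60 | 6.5 | 54.6 | 8.4 | 2.5 |
| 50% | 50% | 120 | 3.3 | 56.3 | 17 | 5.5 |

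Ratios are taken within each scenario from unrounded counts. At a 10-minute gap they run from about 8 to 40 to 1. Dividing the extreme counts across scenarios (32.4/6.5 and 57.2/0.9) would give a looser bracket of about 5 to 60. At a 30-minute gap they run from about 2.5 to 13 to 1.

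**4. Columns and timing key.** Section 3.7 includes Saline and Section 7.2 does not; both cannot describe the same tables. Within Section 7.2, reporting and onset are used in adjacent sentences.

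**5. Dose comparison.** IC High and IC Low are randomized and share the same follow-up schedule, so the unequal windows do not affect that contrast.

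**The case against.** The safety objective is the profile of IC, not a contrast with saline, and no AE test is planned. If the Section 7.2 columns govern, no saline column is shown and nobody is misled by one. Charging all post-IC events to IC is cautious towards the drug, and a table by relationship is planned. This limits the consequence. It leaves the contradiction with Section 3.7 and the question of where saline-mapped events go. The relationship table also depends on judgement in an open-label study, in which the surgeon knows saline from IC (Section 5.1).

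Three stronger readings are tempting, and the documents do not support them.

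- *Events are assigned by report time as a settled rule.* The missing-data sentence refers to onset, and in the IC limb reporting is mentioned only for follow-up events. This is an ambiguity. Heart rate and rhythm are also monitored continuously during the procedure, and clinically significant changes become AEs (Section 7.4), so those events need not wait for the patient to speak.
- *No planned table offers a matched comparison with saline.* Vital signs are taken just before and 5 minutes after each injection, and Table 14.3.4.1 summarises them by timepoint for IC High, IC Low and Saline. The gap is mainly in events such as rash, dyspnea and bronchospasm.
- *Subject counts will differ by thousands to one.* That needs a constant hazard over a month. Early clustering cuts the ratio by about two orders of magnitude; the direction remains.

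It is also fair to say that equal windows would not make the comparison clean. Saline always comes first, so treatment stays tied to stage of procedure.

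**Conclusion.** The point holds as a limit on interpretation with a cheap remedy. Any saline-versus-IC AE comparison under the Section 7.2 mapping is confounded with the rest of surgery and recovery. In every scenario examined an IC excess appears with no drug effect: thousands to one under a constant hazard, about 8 to 40 to 1 with early clustering at a 10-minute gap, and about 2.5 to 13 to 1 with early clustering at 30 minutes. The 10 minutes is inferred from the video, and the 30 minutes, the AE proportions and the clustering are assumptions. The direction does not depend on them.

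A reader might infer that the AE data as a whole cannot be interpreted. That goes too far: IC High versus IC Low stands, and the 5-minute vital signs give a matched view of acute haemodynamic change. The mixed timing key and the conflicting columns are drafting faults that need correcting whether or not anyone intends to compare IC with saline.

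**What to change.** 1. In Section 7.2, define TEAEs and the saline/IC mapping by date and time of onset or worsening, and drop reporting as a key.
2. Reconcile the AE columns in Sections 3.7 and 7.2, and state where saline-mapped events appear.
3. Add one descriptive TEAE and special-interest AE table limited to onset within equal windows after each injection, for example 10 minutes, with the saline window ending at the IC injection if that comes earlier. Show Saline split by later IC dose, IC Low and IC High. Its main use is for events such as rash, dyspnea and bronchospasm.
4. State that the full-period TEAE tables support IC High versus IC Low and not IC versus saline.

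The cost is SAP wording and one table. Injection times are already recorded to the second (Section 3.8.3), and Section 7.2 already refers to onset date and time. Whether the eCRF collects a clock time for AE onset cannot be seen from these documents; events without one must be shown as unplaced. Few events are expected in such short windows, and the fixed order remains a confounder, so the table should carry no test and should say so in a footnote.
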